The age distribution of patients who have a troponin measured will be compared with that of the general population using the World Health Organisation (WHO) population estimates for the UK.

Troponin data

Assay performance

Each Trust measures either troponin I or T using either contemporary or high-sensitivity assays. These tests yield results in different measurable ranges with unique cut-off points for the 99th percentile of the upper limit of normal (ULN). A summary table of the performance of each assay will be assembled.

Handling of troponin data

The study dataset will comprise all patients who have had a troponin measured at each of the five academic centres between 2010 (2008 for University College Hospital) and 1st April 2017.

In clinical practice, troponin levels are frequently dichotomised into “positive” (meaning above ULN) or “negative”. Troponin levels may have a progressive relationship with prognosis, too, but the shape of this relationship is not known across the full spectrum of values and making the assumption of a linear relationship of mortality with troponin (or log troponin) may not be secure.

For these reasons, we will treat the data in two ways.

1. We will dichotomise the peak troponin level as being either positive or negative based on the ULN for each troponin assay. This makes no assumption of the shape of the relationship.
2. To standardise the many troponin assays, we will scale the results using the ratio of the observed troponin value divided by the ULN for that particular troponin assay. For example, a patient with a troponin value of 96 using an assay which has an ULN of 40 would have a scaled result of $96/40 = 2.4 \text{ xULN}$.

In some hospitals and some assays, troponin values above a certain level are systematically reported as “more than X”. According to what the hospitals have reported so far, the threshold at which the system gives results like this is in all cases very high. In no case does this truncation of results occur below 10,000 xULN. We therefore plan to set the uppermost band to be “>10,000 x ULN”. This ensures that the unavailability of an explicit value does not affect the troponin band into which any result is allocated.

Similarly, no hospital has reported truncating lower values of troponin at a threshold that is higher than $\frac{1}{2} \text{ xULN}$. Therefore, we plan for the lowermost band to be “< $\frac{1}{2} \text{ xULN}$ ”.

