Troponin has a marked positive skew. Therefore, we plan for the bands to be spaced not arithmetically but exponentially, with narrow spacing nearer low values, where there is a higher frequency density of troponin values.

Adopting this approach for analysis has the following advantages:

1. It allows the shape of the relationship to be explored without making assumptions about the shape in advance.
2. It allows values documented in the hospital databases as “less than X” or “more than X” to be used correctly in the analysis rather than omitted or have imputed values.
3. The resulting display of the mortality relationship should be easily interpreted and applied by clinicians.

All analyses on troponin will be performed using the peak troponin level. For patients who have a single troponin measurement, the peak troponin will be based on this measurement. In the remainder of the patients who have more than one

troponin test in the same hospital episode, the peak troponin value will be defined as the highest of all measurements.

Relationship between troponin positivity, age and mortality

To assess the association of dichotomous troponin level (above ULN or not) with all-cause mortality, Cox proportional hazards regression modelling will be used. Hazard ratios will be determined for the following age groups: 18-29, 30-39, 40-49, 50-59, 60-69, 70-79, 80-89 and 90+ years. We will also stratify the hazard ratios for troponin positive versus negative groups across these age groups by troponin assay (contemporary versus high-sensitivity troponin assay).

The Kaplan-Meier method will be used to calculate and display cumulative mortality, with positive and negative troponin bands compared using the log-rank statistic.

Relationship between troponin level and mortality

The main analysis of the association of progressively higher troponins with all-cause mortality will be performed without making assumptions about the shape of the relationship, i.e. with Cox proportional hazards regression modelling.

The Kaplan-Meier method will be used to calculate and display cumulative mortality, with troponin bands compared using the log-rank statistic. The results will be stratified according to ACS diagnosis and revascularisation status.

ACS diagnosis

The ICD-10 codes in Table 2 will be used to indicate an ACS diagnosis.

ICD-10 Code	Category
I20.0	Unstable angina
I21.0	Acute transmural myocardial infarction of anterior wall

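### The main troponin-level Cox model states no age adjustment, so the mortality gradient across troponin bands could partly reflect age

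*Combined protocol and SAP*

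**What the plan says.** *Relationship between troponin level and mortality* begins: "The main analysis of the association of progressively higher troponins with all-cause mortality will be performed without making assumptions about the shape", with Cox regression as the method. That sentence does not mention bands. *Handling of troponin data* explains, however, that results scaled to each assay's upper limit of normal will be grouped in bands so that the shape can be explored, so I read the main analysis as a Cox model with bands as the exposure. Neither section lists a covariate. A Kaplan-Meier display follows, "with troponin bands compared using the log-rank statistic", and then: "The results will be stratified according to ACS diagnosis and revascularisation status".

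Age is used in the preceding section, headed "Relationship between troponin positivity, age and mortality". There the exposure is positive versus negative troponin, and the plan says "Hazard ratios will be determined for the following age groups", of which there are eight, from 18-29 to 90+. That section has its own Kaplan-Meier display, "with positive and negative troponin bands compared using the log-rank statistic".

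*Primary outcome* is all-cause mortality. *TROP-RISK STUDY dataset* provides age in years at the first troponin test. No section contains a general rule on covariates.

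**The concern.** Age is an obvious potential confounder when the outcome is death from any cause, and the plan itself reports the positivity hazard ratios by age group. Yet the analysis it calls main for troponin level would, followed as written, compare bands with whatever age mix each happens to contain.

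The shape of the gradient is what is at stake. *Handling of troponin data* motivates the banding by noting that "the shape of this relationship is not known across the full spectrum of values", and it lists as an advantage that "The resulting display of the mortality relationship should be easily interpreted and applied by clinicians". A clinician with a patient of known age is likely to read a band's hazard ratio as what the troponin result adds to that knowledge. A crude hazard ratio does not answer that question, and the plan does not label it as crude.

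**Working it through.** **1. The text, analysis by analysis.**

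| Analysis | Age stated? | Other stratifiers stated |
|---|---|---|
| Positivity, Cox | Yes, hazard ratios in eight age groups | Assay type |
| Positivity, Kaplan-Meier and log-rank | Not stated, though the section heading names age | None |
| Troponin level, Cox (main) | No | ACS diagnosis, revascularisation status |
| Troponin level, Kaplan-Meier and log-rank | No | ACS diagnosis, revascularisation status |

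The plan states no sample size, event count or effect size, so it has no figure to reproduce. What follows is illustration, and every input is assumed.

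**2. A rough rule.** If log hazard rises by b per year of age and one band is D years older on average than another, then approximately

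crude HR ≈ (HR at a given age) × exp(b × D).

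Take b from 0.06 to 0.10 and a true HR of 1:
- D = 2: exp(0.12) = 1.13 to exp(0.20) = 1.22.
- D = 5: exp(0.30) = 1.35 to exp(0.50) = 1.65.

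The factor is above 1 for an older band and below 1 for a younger one. Age could therefore steepen, flatten or bend the gradient.

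**3. Simulation without ACS or revascularisation.** The assumptions were:
- 40,000 patients in the plan's eight age groups, with shares 6, 9, 12, 16, 18, 19, 15 and 5%.
- Death rate 0.06 per year at age 70-79, multiplied by h per age group.
- Troponin positive in 35% at age 60-69, with odds multiplied by o per age group.
- Censoring uniform over 0 to 7 years, and no troponin effect within any age group.

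Each cell shows the crude HR, then the HR stratified by the eight age groups:

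| h | o = 1.0 | o = 1.2 | o = 1.5 | o = 1.8 |
|---|---|---|---|---|
| 1.5 | 1.03 / 1.02 | 1.24 / 1.01 | 1.55 / 0.99 | 1.75 / 0.96 |
| 2.0 | 1.01 / 0.99 | 1.39 / 1.00 | 1.94 / 1.02 | 2.37 / 0.99 |
| 2.5 | 1.00 / 0.99 | 1.47 / 1.04 | 2.08 / 0.99 | 2.65 / 0.98 |

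When positivity is unrelated to age (o = 1.0), the crude HR is 1.00 to 1.03. Otherwise it is 1.24 to 2.65. Risk here is constant within each age group, so stratifying by those groups is bound to remove the age effect.

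**4. Simulation with ACS and revascularisation as strata.** Age was continuous, there were two troponin levels, b was 0.06 to 0.10 and the true HR was 1. The HR for the higher against the lower level, stratified by ACS and revascularisation only, was:
- 2 years older: 1.09 to 1.25.
- 5 years older: 1.30 to 1.55.
- 5.5 years younger: 0.68 to 0.82.

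Adding the eight age groups as strata gave 0.97 to 1.04, and adding an age spline instead gave 0.97 to 1.03. Under these assumptions the plan's two stratifiers do not stand in for age, and the two forms of age adjustment work about equally well.

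**The case against.** **A crude gradient is legitimate.** The plan speaks of association and prognosis and makes no claim of an effect independent of age. This stands as a reason to keep unadjusted hazard ratios. It does not excuse presenting them unlabelled, as the main result, with nothing adjusted beside them.

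**The log-rank tests.** A reader might infer that both are faulty because neither is stated to be stratified by age. The documents do not support that. An unstratified log-rank test is the matching test for unstratified Kaplan-Meier curves. If bands differ in age and age drives death, their crude survival really differs, and a small p-value is a correct rejection, not a false positive. For positivity, the hazard ratios within eight age groups already deal with age, and the section heading suggests that curves by age group may be intended.

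**What stratifying means here.** The plan does not say whether the ACS and revascularisation sentence covers the Cox model or only the curves. Nor does it say whether results are reported separately or the factors enter as strata. In the preceding section similar wording about assay type most naturally means separate reporting. The simulation in step 4 takes one reading, so its figures depend on that choice. Age is absent on either reading.

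**The form of adjustment.** One age-adjusted hazard ratio per band averages over any interaction between age and troponin. If ACS and revascularisation were each yes/no and all factors were crossed, eight age groups would give 8 × 2 × 2 = 32 strata, which could be sparse in the highest bands. Both remarks stand. They bear on how to adjust, not whether to.

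**Adjustment may be intended.** It may be, but it is not written, and an unwritten choice can be made after results are seen.

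**Conclusion.** The point holds for the main troponin-level Cox analysis. No age term is stated, ACS diagnosis and revascularisation status do not replace one, and no rule elsewhere fills the gap. If bands differ in age, the band hazard ratios and the shape of the gradient will partly reflect age.

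The conclusion about the text is firm. The size is not: the documents report neither age by band nor death rates by age, so magnitude and direction in this cohort are unknown. The simulated figures show what could happen, not what is likely.

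A reader might go further and infer that the gradient could be entirely an age effect. That is seen only in runs where the true hazard ratio was set to 1, and nothing in the documents supports it. Nor does the point extend to the positivity Cox analysis. It should be fixed because it affects how the main result is read and the remedy is cheap.

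**What to change.** In *Relationship between troponin level and mortality*, state that:

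- The main banded Cox model is adjusted for age at first troponin. Choose one form in advance: a flexible continuous term such as a spline, or the plan's eight age groups as strata. If ACS and revascularisation are also to be strata, the continuous term avoids multiplying the cells.
- Unadjusted band hazard ratios are reported beside the adjusted ones and labelled as unadjusted.
- The Kaplan-Meier curves and their log-rank tests stay as planned, labelled as crude and descriptive. Age-stratified log-rank tests are optional.

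The cost is a few sentences and a few lines of analysis, with no new data. The database freeze was set for 1 April 2017 and the document was updated on 04/07/2024, but the documents do not say whether analyses have been run. If they have, label the age-adjusted model as added later.

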death or be able to calculate it from other information (all dates are provided as delta for first troponin). The provision of date of death has been agreed by each of the information governance offices at each of the sites in the following de-identification and anonymisation protocol for the TROP-RISK STUDY:

- The exact date of death is required to evaluate mortality after diagnosis.
- Patients presenting with acute coronary syndromes have a high frequency of cardiac events and a high short-term mortality rate. An accurate measure of death is therefore required to fully evaluate this.
- To redact the date of death to year only would misrepresent the survival of these patients, particularly for those who survive for less than one year. The clinical leads at our BRCs have underlined the importance of having the date in full for the TROP-RISK study.

Demographic	Anonymisation
Local Identifier	Provided if NHS number is missing
NHS Number	Use local pseudonymisation algorithm (key to be retained at source) Rename field to subject ID
Family Name	To be removed – LOCAL use
Given Name	To be removed – LOCAL use
Date of Birth	YYYY
Date of Death	DD-MM-YYYY

Table 1. Anonymisation of data elements

Data validity and quality

Prior to pseudonymisation within the clinical systems, NHS number, Date of Birth and patient names will be automatically checked to remove duplication of patients. Samples of data will be clinically validated by members of the clinical team to ensure that the transformation process is correct and data are attributed to the correct patients prior to pseudonymisation. After clinical validation is complete, the data will be transformed to a standardised XML format and validated (Figure 1).

[figure not shown]

Figure 1. Data import and validation process.

Data sharing between Trusts

Data are shared in accordance with the SOP for data sharing, as outlined in Section 1.3.2. Data are encrypted in transit via sFTP on the N3 network (Figure 1). The sFTP is set up and hosted by ICHNT.

Procedures for secure research database

Data validity and quality

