Data access for research

TROP-RISK STUDY dataset

All analyses for the TROP-RISK STRUDY will be completed on fully de-identified data. This includes further de-identification to remove dates.

A designated clinical researcher ([name]) will freeze a copy of the database on 1st April 2017, so a static dataset can be used for analysis. This will be retained separately from the live database to allow reproducible analyses.

The study dataset will comprise all patients who had a troponin measured at each of the five academic centres between 2010 (2008 for University College Hospital) and 2017.

Dates will be converted to delta dates, with date zero being the date of the first troponin test. All further dates are provided as number of days from date zero. Age will be provided in years, at the time of the first troponin test.

Date of death will be converted to the number of days since date zero. All patients will be retrospectively followed up, using routinely collected data on the NHS Spine Application, Summary Care Record, until death or censoring on 1st April 2017.

Data elements

The database model will include 156 data points, grouped into demographics, emergency department attendance and inpatient episodes, biochemistry, diagnosis, angiography, revascularization, echocardiography and mortality. Diagnostic data will be based on International Statistical Classification of Diseases and Related Health Problems (ICD) discharge codes.

Outcomes

Primary outcome

The primary outcome will be all-cause mortality. The nature if the data sources means that this is the outcome that will be available and it will be available with high fidelity.

Secondary outcomes

The secondary outcomes will be:

- Acute coronary syndrome (ACS) diagnosis (unstable angina, non-ST segment elevation myocardial infarction (NSTEMI), ST-segment elevation myocardial infarction (STEMI))
- Non-ACS diagnosis
- Angiography
- Revascularisation (coronary artery bypass grafting CABG), percutaneous coronary intervention (PCI))

Statistical Methods

Baseline data

Baseline and demographic characteristics will be summarised by standard descriptive summaries:

- means (standard deviation) for continuous variables which are normally distributed
- median (interquartile range) for continuous variables which are not normally distributed
- number (percentage) for categorical variables

Age distribution

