I21.1	Acute transmural myocardial infarction of inferior wall
I21.2	Acute transmural myocardial infarction of other sites
I21.3	Acute transmural myocardial infarction of unspecified site
I21.4	Acute subendocardial myocardial infarction
I21.9	Acute myocardial infarction, unspecified
I22.0	Subsequent myocardial infarction of anterior wall
I22.1	Subsequent myocardial infarction of inferior wall
I22.8	Subsequent myocardial infarction of other sites
I22.9	Subsequent myocardial infarction of unspecified site
I24.8	Other forms of acute ischaemic heart disease
I24.9	Acute ischaemic heart disease, unspecified

Table 2. ICD-10 codes used to indicate an ACS diagnosis

Revascularisation status

Acute revascularisation will be defined as having PCI or CABG in the time window between 48 hours before and 3 months after the first troponin measurement. This will account for patients who had revascularisation, in particular PCI, as an

emergency prior to their first troponin blood test and to capture revascularisation, in particular CABG, performed as an outpatient following their index admission.

Statistical package

Statistical analyses will be performed using SPSS software version 24 (SPSS Inc., Chicago, Illinois, United States) and the results verified by replicate analysis using R 3.3.2 statistical package (the R Core Team, Vienna, Austria).

Statistical significance

All hypothesis tests will be 2-tailed. A p-value of <0.05 will be considered statistically significant. No correction will be implemented for multiple testing.

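### Revascularisation strata count procedures up to 3 months after the survival clock starts, so their Kaplan-Meier curves carry immortal time that flatters the revascularised stratum

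*Combined protocol and SAP*

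**What the plan says.** The document is the combined protocol and SAP.

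- **Time origin** (TROP-RISK STUDY dataset): "Dates will be converted to delta dates, with date zero being the date of the first troponin test". The section adds "All further dates are provided as number of days from date zero", and death is likewise expressed as days since date zero. Follow-up ends at death or on 1 April 2017.
- **Stratified display** (Relationship between troponin level and mortality): cumulative mortality is shown by Kaplan-Meier, and troponin bands are compared by log-rank. Then: "The results will be stratified according to ACS diagnosis and revascularisation status".
- **Stratum definition** (Revascularisation status): a patient counts as acutely revascularised by "having PCI or CABG in the time window between 48 hours before and 3 months after the first troponin measurement". The window starts before the test to include emergency PCI, and extends to 3 months "to capture revascularisation, in particular CABG, performed as an outpatient following their index admission".

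The plan contains no landmark, delayed entry, time-dependent covariate or separate handling of early deaths.

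**The concern.** The stratum is decided by events that happen after the clock has started. To enter the revascularised stratum through a procedure on day *k*, a patient must be alive on day *k*, so the time from 0 to *k* is immortal. Someone on the same pathway who dies first is moved to the other stratum. Deaths are removed from one curve and added to the other, so neither curve estimates the mortality of an identifiable group at presentation.

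The misplaced deaths are the early ones, and the De-identification section says of this population: "Patients presenting with acute coronary syndromes have a high frequency of cardiac events and a high short-term mortality rate". The Handling of troponin data section says of its banded analysis: "The resulting display of the mortality relationship should be easily interpreted and applied by clinicians". That sentence concerns troponin and mortality, but it is this display that is then stratified. A clinician shown panels by revascularisation status could take part of the gap for benefit when it comes from the classification rule. If timing or frequency of procedures varies with troponin, the band comparisons inside each stratum can also be distorted.

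**Working it through.** The plan states no figure to reproduce: it gives no procedure timing, revascularised share or mortality rate. The window, origin and stratification come from the plan. All other inputs are assumptions, and 3 months is taken as 90 days.

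**Set-up, with no true effect of revascularisation**

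Let *p* be the share planned for a procedure, *F(t)* the proportion of planned procedures done by day *t*, *S(t)* survival and *f(t)* the death density, the same for everyone. A planned patient who dies on day *t* is classed as revascularised with probability *F(t)*. With A = ∫₀⁹⁰ f(t)F(t)dt and D = 1 − S(90), apparent 90-day mortality is

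- revascularised: A / [A + S(90)]
- not revascularised: (D − pA) / [D − pA + (1 − p)S(90)]

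If every procedure is at or before date zero, F = 1, A = D, and both expressions equal D, so there is no bias. Any later procedure makes A smaller than D.

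**Worked example**

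Assume p = 10%, half of procedures at or before date zero, the rest uniform over days 0–90, and 30-day mortality 6%. The hazard is h on days 0–30, h/3 on days 30–90 and h/12 afterwards.

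- h = −ln(0.94)/30 = 0.0020625 per day
- S(90) = exp(−30h − 60h/3) = exp(−50h) = 0.9020, so D = 9.8%
- Mean of S over days 0–90 = (29.09 + 55.25)/90 = 0.9371, where 29.09 = 0.06/h and 55.25 = 0.94 × [1 − exp(−20h)]/(h/3)
- A = 0.5 × 0.0980 + 0.5 × (0.9371 − 0.9020) = 0.0666
- Revascularised: 0.0666/(0.0666 + 0.9020) = **6.9%**
- Not revascularised: (0.0980 − 0.0067)/(0.0913 + 0.9 × 0.9020) = 0.0913/0.9031 = **10.1%**

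If the later procedures are instead 70% exponential with mean 3 days and 30% uniform over days 5–90 (the mix), the curves show **8.7% versus 9.9%**.

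**Range**

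The same calculation on a 0.05-day grid covered 180 scenarios: p of 10, 25 or 50%; 0, 20, 50, 75 or 90% of procedures at or before date zero; 30-day mortality 1, 3, 6 or 10%; and later procedures exponential (mean 3 days), the mix, or uniform. The table gives the limiting Cox hazard ratio, revascularised versus not. It is a reading aid, not a planned test, and the true value is 1.00.

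| At or before date zero | 90 days | 3 years | 90 days, uniform dropped | 3 years, uniform dropped |
|---|---|---|---|---|
| 20% | 0.33–0.95 | 0.65–0.98 | 0.68–0.95 | 0.85–0.98 |
| 50% | 0.52–0.97 | 0.77–0.99 | 0.78–0.97 | 0.90–0.99 |
| 90% | 0.88–0.99 | 0.95–1.00 | 0.95–0.99 | 0.98–1.00 |

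Over all 180 scenarios the hazard ratio is 0.23–0.99 at 90 days (median 0.89) and 0.59–1.00 at 3 years (median 0.95). A day-90 landmark gives 1.00 in every one.

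**Independent simulation**

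This used 400,000 patients per scenario, 30% planned, constant hazard to day 90 and uniform later timing. At 10% true 90-day mortality the strata showed 9.2% versus 10.4%, 7.5% versus 10.9% and 6.2% versus 11.7% with 80, 50 and 20% of procedures at or before date zero. The 90-day hazard ratios were 0.88, 0.68 and 0.51. With all procedures at or before date zero, the hazard ratio was 1.00. Across all mortality levels, a landmark gave 0.98–1.02 and a time-dependent term 0.99–1.02.

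**Troponin hazard ratio within strata**

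Assumed: follow-up to 1 year, true value 2.24, 30% troponin-positive, 30-day mortality 1–6% in troponin-negatives, and later procedures following the mix or uniform pattern.

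| Procedures in positives versus negatives | Revascularised | Not revascularised |
|---|---|---|
| Same timing and share | 2.24–2.26 | 2.19–2.24 |
| Earlier (80% vs 20% at or before date zero) | 2.50–3.20 | 1.80–2.22 |
| Later (20% vs 80%) | 1.59–2.01 | 2.26–2.77 |
| More often planned (40% vs 5%, or 50% vs 10%) | 2.24–2.26 | 2.26–3.05 |

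The landmark returns 2.24 in each case.

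**The case against.** The strongest reply is that revascularised versus not revascularised is never tested or named as an aim. Revascularisation is listed as a secondary outcome, the log-rank test compares troponin bands, and stratified results may simply mean separate panels. The plan also never states that these Kaplan-Meier curves start at date zero. Within strata, the troponin hazard ratio barely moves when procedure timing and share do not depend on troponin. The lowest hazard ratios all need uniform timing, a stress case given that the plan itself expects emergency PCI before the first test. If 90% of procedures are at or before date zero, the bias is small.

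Most of this limits the size and reach of the problem without removing it. Date zero is the only origin the plan gives, and every date is supplied relative to it, so the inference about the clock is the natural one. Separate panels do not help, because each stratum's absolute mortality is wrong by itself. Dropping uniform timing leaves bias in the same direction. The bias vanishes only if no procedure follows date zero, which contradicts the stated reason for the 3-month window. Two limits stand: the documents cannot place the truth within the ranges, and the effect on within-stratum troponin comparisons has unknown size and direction.

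**Conclusion.** The concern holds for the revascularisation-stratified results and should be fixed. Followed as written, the plan lowers the revascularised mortality curve and raises the other. The direction is certain; the size is not, because it depends on the share of procedures after date zero, their delay and early mortality, none of which the documents give. Under the stated assumptions the distortion ranges from negligible, when nearly all procedures are at or before date zero, to several percentage points of 90-day mortality when many are delayed. Troponin hazard ratios within strata are nearly unaffected unless procedure timing or frequency depends on troponin; if it does, they can move either way. The whole-cohort troponin, age-group and assay analyses do not use this variable and stand.

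**What to change.** Change only the revascularisation-stratified results.

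1. **Landmark.** Take patients alive and under follow-up at day 90, classify them by procedures up to then, and run Kaplan-Meier and Cox from day 90. Define 3 months as a fixed number of days.
2. **Early deaths.** Report days 0–90 separately by troponin band, without splitting by eventual revascularisation.
3. **Alternative.** Treat revascularisation as time-dependent, with person-time before the procedure counted as not revascularised. This keeps all patients. Because times are held in whole days, state a rule for a death and a procedure on the same day.
4. **If the date-zero strata are also kept,** label them as subject to immortal time. Patients first tested after 1 January 2017 lack a full window before censoring on 1 April 2017 and may be classed as not revascularised by default. They are about 3.4% of patients if intake was even from January 2010 (90 of 2,647 days), ignoring the 2008 start at one site. They drop out of the landmark set without a special rule.
5. **Interpretation.** State that confounding by indication remains under either method, so the strata do not estimate a treatment effect.

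The cost is SAP wording and a short re-analysis, since the dates needed are already held relative to date zero. The drawback of the landmark is that its results apply to 3-month survivors only, which is why the separate early-mortality report is needed.

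### Acute revascularisation is defined by timing alone, so planned procedures shortly before the first troponin are labelled acute, and their possibly procedure-related peaks enter the troponin bands unflagged

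*Combined protocol and SAP*

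**What the plan says.** Four parts of the combined protocol and SAP bear on this point.

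- **Revascularisation status.** The acute category is "having PCI or CABG in the time window between 48 hours before and 3 months after the first troponin measurement". The window is meant to cover revascularisation, chiefly PCI, done as an "emergency prior to their first troponin blood test and to capture revascularisation", chiefly CABG, carried out on an outpatient basis later.
- **TROP-RISK STUDY dataset.** "The study dataset will comprise all patients who had a troponin measured at each of the five academic centres". Handling of troponin data repeats this. Neither section sets a condition on why the test was ordered.
- **Handling of troponin data.** Every troponin analysis uses the peak. Where an episode has several tests, "the peak troponin value will be defined as the highest of all measurements". Values before and after a procedure are not distinguished.
- **Relationship between troponin level and mortality.** Band results are stratified by ACS diagnosis and by revascularisation status. The plan does not say whether the two factors are crossed or taken one at a time.

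The documents do not mention planned procedures, troponin release caused by a procedure, how often either occurs, or the mortality of such patients.

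**The concern.** The reason given for the look-back is emergency treatment, but nothing in the rule enforces it: there is no urgency, indication or ACS-code condition. Someone admitted for a planned PCI or CABG whose first troponin is taken the next day meets the definition of acute revascularisation.

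For that patient every troponin in the episode was taken after the procedure, so the peak may reflect the procedure and not a spontaneous event. That PCI and CABG can release troponin is general clinical knowledge, used here as an assumption; the documents do not discuss it. The peak is nevertheless banded in xULN beside spontaneous injury.

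Two results are at stake. One is the shape of the troponin-mortality relationship, which the plan wants to explore without prior assumptions and present in a form clinicians can use. The other is the set of band results within the revascularised stratum, which would mix emergency and planned cases under one label.

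**Working it through.** The plan gives no sample size, event count or effect size on this point, so there is no figure of its own to reproduce. The check has three steps.

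**1. Which rule does what.** Take a planned procedure on day −1 and a first troponin on day 0.

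- Entry to the dataset follows from having a troponin.
- The band follows from the peak divided by the assay's ULN.
- The acute label follows from the time window.

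Narrowing the window rule changes only the label. The patient keeps the same peak and band, and every whole-cohort hazard ratio is unchanged. There are thus two separate gaps: a label that does not match its stated purpose, and a peak that carries no flag for sampling after a procedure. The second gap is wider than the look-back, because a procedure after the first troponin in the same episode can also raise the peak.

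**2. Could the band results move, and which way?** All inputs here are assumptions. Let T be the high-versus-low-band hazard ratio among other patients, fH and fL the shares of planned-procedure patients in the high and low bands, and h their hazard relative to other low-band patients. By simple mixing of rates:

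observed HR = [(1 − fH)·T + fH·h] / [(1 − fL) + fL·h]

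With T = 3:

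| fH | fL | h = 0.3 | h = 1 | h = 3 | h = 4 |
|---|---|---|---|---|---|
| 10% | 0 | 2.73 | 2.80 | 3.00 | 3.10 |
| 20% | 0 | 2.46 | 2.60 | 3.00 | 3.20 |
| 30% | 0 | 2.19 | 2.40 | 3.00 | 3.30 |
| 10% | 10% | 2.94 | 2.80 | 2.50 | 2.38 |
| 10% | 30% | 3.46 | 2.80 | 1.88 | 1.63 |
| 20% | 30% | 3.11 | 2.60 | 1.88 | 1.68 |

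Worked cell (10%, 30%, h = 0.3): (0.9 × 3 + 0.1 × 0.3) / (0.7 + 0.3 × 0.3) = 2.73 / 0.79 = 3.46.

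With none in the low band, the ratio is attenuated if h < T, unchanged if h = T and steeper if h > T. It is also steeper when low-risk planned patients are commoner in the low band than in the high band. Attenuation is the commoner result in this table, but the inputs were chosen, not observed.

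A scenario built to attenuate shows how large the effect could be. Assume 1-year mortality of 5% in the reference band, 20% or 30% among other high-band patients, 1% to 3% among planned-procedure patients, and no planned-procedure patients in the reference band. Band mortality is m = (1 − f)·m_other + f·m_planned, and HR = ln(1 − m)/ln(0.95).

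| m_other | f = 0 | f = 10% | f = 30% |
|---|---|---|---|
| 20% | 4.35 | 3.89 to 3.94 | 3.01 to 3.15 |
| 30% | 6.95 | 6.16 to 6.22 | 4.67 to 4.82 |

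The 30% share has no basis in the documents.

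**3. What the strata already do.** A planned case without a Table 2 code falls in the non-ACS stratum whether or not the factors are crossed, so the ACS-stratum results are largely protected. If the factors are crossed, such cases are confined to the non-ACS revascularised cell. If not, they also sit in the revascularised stratum as a whole. The unstratified band analysis contains them in either case.

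**The case against.** The strongest reply is that revascularisation status is only a stratifier, that stratifying by ACS diagnosis already separates most planned cases, and that an all-comer cohort is a deliberate choice. All three points stand. They are reasons to keep the all-comer analysis as primary and not to exclude patients from it. They do not repair the label, and they do not show a reader how far the unstratified result depends on post-procedure values.

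The forward window also has no urgency condition. There, however, the plan says that it means to include later outpatient CABG, so the label matches its purpose. The mismatch lies in the look-back.

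Three stronger readings are tempting, and the documents do not support them:

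- **That the revascularisation rule puts planned patients into the high bands.** It does not; the cohort and peak rules determine the band. Nor do the documents say how high post-procedure values reach.
- **That the relationship must be flattened or show a plateau.** This needs planned patients to be concentrated in the higher bands and to die less often than others there. Troponins here come from routine care, so a first test after a planned procedure may have been sent for a suspected complication, which would mark a higher-risk group. A plateau would also need the planned share to rise across successive bands enough to offset rising mortality, and a two-band calculation cannot show that.
- **That acute revascularisation will appear to improve survival.** The plan states no comparison of revascularised with non-revascularised patients; it stratifies the band results.

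A practical objection also stands: research dates are held in whole days, so the order of a procedure and a troponin on the same day may not be recoverable.

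**Conclusion.** The point holds in a limited form. The acute label rests on timing alone and does not enforce the emergency purpose given for the look-back, so a planned procedure within 48 hours before the first troponin is mislabelled. Separately, the all-comer cohort and the peak rule let a possibly procedure-related troponin into the bands with no flag and no sensitivity analysis.

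This can distort the troponin-mortality relationship and blur the revascularised stratum. Attenuation is plausible, but neither its size nor its direction is established: under the assumptions above, a ratio of 3 is observed anywhere from 1.63 to 3.46. Whether it matters depends on three quantities that the documents do not give: how common these patients are, which bands they fall in, and how often they die. The point does not undermine the primary analysis. It is worth acting on because the change is small and the result would show whether the bands depend on these patients.

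**What to change.** 1. In Revascularisation status, count a procedure dated before the first troponin as acute only if the index episode carries a Table 2 code or began with an emergency department attendance. Flag the remainder as 'first troponin after non-emergency procedure'.
2. Keep the all-comer Cox and Kaplan-Meier band analyses as primary. Add a pre-specified sensitivity analysis that excludes flagged patients and, where a procedure follows the first troponin in the same episode, takes the peak from pre-procedure values only.
3. Report ACS diagnosis and revascularisation status as crossed strata.
4. State how a procedure and a first troponin on the same day are handled.

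The cost is a short addition to the definition, one flag and one repeat analysis. Diagnosis, emergency department attendance, revascularisation and biochemistry are among the data groups listed under Data elements. The individual fields are not shown, so their availability should be confirmed. The downside is that some genuine emergencies with neither an ACS code nor an emergency department record will be flagged. Because the all-comer analysis stays primary, they are lost only from the sensitivity analysis, though they also lose the acute label.
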